A Introduction

A1 Study Abstract:

This study will use non-invasive MR scanning to help answer questions related to brain function and development in children suffering from craniosynostosis. Craniosynostosis affects roughly 1 in 2000 children. Primary indication for operative treatment for patients with craniosynostosis is to prevent or treat increased Intra-Cranial Pressure (ICP) and avoid neurological impairment. Increased ICP is thought to result from restricted space for brain growth caused by the abnormal cranial vault. However, the literature on the relationship between craniosynostosis and ICP is limited. Due to the invasiveness of the test, preoperative ICP monitoring is not routinely performed to decide if operative repair is required. Other indirect signs of elevated ICP have been described but are not reliable.

While it is not currently feasible to measure ICP directly, we may be able to indirectly determine ICP in children via magnetic resonance imaging (MRI). We aim to compare the assessment of ICP with the conventional, invasive intraventricular shunt to an indirect assessment of ICP via MRI.

Ten children with an intraventricular shunt will be enrolled in this pilot study over a one-year period. We will obtain indirect measures of ICP. The results will be compared to ICP measures obtained via the shunt.

Ultimately the assessment of ICP using MRI in patients with craniosynostosis may revise surgical indications and timing of surgery, potentially changing the standard of care for patients with craniosynostosis. Additionally, this approach might be used for patients with other diagnoses which impact ICP.

A2 Primary Hypothesis

Indirect (via MRI) and direct measures of ICP will have a significant positive correlation.

A3 Purpose of the Study Protocol

The purpose of this study is to evaluate the use of magnetic resonance imaging (MRI) to determine intra-cranial pressure in young children.

B Background

B1 Prior Literature and Studies

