Although multiple tests have been suggested to assess ICP in patients with craniosynostosis, including papilledema and copper beaten appearance of the skull on plain film, none have been shown to be reliable measures or markers of ICP. Recent advances in MRI suggest that ICP can be indirectly measured with this modality non-invasively and with minimal patient risk.

D Investigational Agent

D1 Clinical Data to Date

The MR sequences for this study have been used in studies of traumatic brain injury. To our knowledge these sequences have not yet been used for patients with craniosynostosis.

D2 Dose Rationale and Risk/Benefits

The main risk of the MR scan in this population is the feeling of being closed in or discomfort from lying still. This is an acceptable risk given the benefit of obtaining hard evidence of brain stress in subjects with synostosis. The time patients are in the scanner (approximately 45 minutes) has been adequate to obtain useful data in populations of minors post traumatic brain injury and normal controls. These tests were performed by Drs. [name] and [name].⁷

E Study Design

E1 Overview or Design Summary

Up to 12 patients with craniosynostosis will be enrolled in this pilot study. Various measures of cerebral metabolism and perfusion will be taken during a single visit via MR scanning.

The results may also be compared to age and gender matched normative data. These controls will be recruited in the plastic surgery clinic and/or deidentified data from normal subjects from another study will be used. Participation in this research study consists of one to two parts. First, all patients will be asked to extend a clinical visit for MRI. During this time the intra-cranial pressure MRI testing will be done, lasting approximately 10 minutes. The scan will be performed in the radiology center on the 1st floor of Children's Hospital. The clinical scan will be done under sedation. Secondly, during the same visit, a transducer will be attached to the participant's intraventricular catheter if it is not already in place. The patients ICP will be measured directly with this transducer. Subjects have no further commitment once the scan (and ICP measurement) is complete.

E2 Subject Selection and Withdrawal

2.a Inclusion Criteria

- Subjects presenting to the Plastic Surgery clinic with unrepaired single-suture craniosynostosis.
- Age-matched controls

Exclusion Criteria

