- Implants (e.g. pacemakers) that might rule out use of MR scanning.

- History of other abnormalities known to affect brain topology or function.
- Control subjects must have no history of craniofacial abnormality or head trauma.

2.b Subject Recruitment Plans and Consent Process

Subjects will be recruited through the Plastic Surgery clinic.

2.c Risks and Benefits

Risks: the risk of discomfort of claustrophobia during the MR scan

Benefits: Future patients with craniosynostosis might benefit from this study because it may lead to a revision of surgical indications and timing of surgery, potentially changing the standard of care for patients with craniosynostosis.

2.d Early Withdrawal of Subjects

Subjects may withdraw at any time before or during the study.

2.e When and How to Withdraw Subjects

Subjects or their parents/guardians may withdraw verbally.

2.f Data Collection and Follow-up for Withdrawn Subjects

There will be no follow-up data collection

F Study Procedures

F1 Screening for Eligibility

Craniosynostosis will be diagnosed via computed tomography performed as part of standard care

F2 Schedule of Measurements

There will be a single visit consisting of the MR scan, performed in the Center for Clinical Imaging Research.

F3 Safety and Adverse Events

3.a Medical Monitoring

Prior to MR scanning, subject's parent or guardian will complete an MRI safety questionnaire. The subject's heart rate and blood pressure will be continuously monitored and recorded every 15 minutes during the MR scan.

3.b Definitions of Adverse Events

Typical adverse events during MR scans are claustrophobia and issues relating to metallic implants.

3.c Data Collection Procedures for Adverse Events

Any adverse events will be duly recorded and noted by the investigators

3.d Reporting Procedures

A summary of any adverse events will be included in continuing review forms sent to the IRB.

3.e Adverse Event Reporting Period

Annually (in the continuing review forms)

F4 Study Outcome Measurements and Ascertainment

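### The 2.a exclusion does not exempt the condition behind a shunt or catheter, so it may remove many or most of the children in whom direct ICP can be read

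*Combined protocol and SAP*

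**What the plan says.** The abstract (A1) describes the sample by its shunt: "Ten children with an intraventricular shunt will be enrolled in this pilot study over a one-year period". It names the comparator too: "The results will be compared to ICP measures obtained via the shunt". The primary hypothesis (A2) is that "Indirect (via MRI) and direct measures of ICP will have a significant positive correlation".

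The design summary (E1) describes the sample by diagnosis: "Up to 12 patients with craniosynostosis will be enrolled in this pilot study". It adds that "Participation in this research study consists of one to two parts". For the direct reading, "a transducer will be attached to the participant's intraventricular catheter if it is not already in place". No section provides for placing a catheter for the study.

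Eligibility (E2, 2.a) admits as cases "Subjects presenting to the Plastic Surgery clinic with unrepaired single-suture craniosynostosis", plus age-matched controls. It mentions neither a shunt nor a catheter. One of its exclusions is "History of other abnormalities known to affect brain topology or function". The separate implant exclusion covers only devices that might preclude MR scanning, so it does not bar shunts as such.

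No section says why a participant would have a shunt or catheter, and none exempts the condition that led to it.

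**The concern.** A2 can be examined only in children who contribute both measurements. The direct one depends on a catheter that the child already has. Where that catheter was placed for a brain condition separate from the craniosynostosis, the natural reading of the 2.a exclusion is that the child is ineligible. The criterion therefore works against the primary hypothesis; it is more than a missing detail.

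Adding a catheter requirement to the inclusion list would not be enough. A child with both single-suture craniosynostosis and a shunt placed for another brain condition would still be turned away.

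There is also a conditional consequence. If such children were enrolled despite the exclusion, G3 would place them among the craniosynostosis cases compared with matched controls, because it defines no separate set for them. The F4 measures (NAA, lactate, oxygen extraction, blood flow, functional connectivity) are presented as markers of injury, metabolism, perfusion and development. A second brain condition could shift them, and a difference from controls could then not be attributed to craniosynostosis.

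**Working it through.** The plan has no power or sample-size figure to reproduce; G1 says that no relevant data exist for one. The check is a comparison of sections, followed by an illustration of size.

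**Sections side by side**

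1. A2 needs paired MRI and direct ICP values in the same child.
2. Direct ICP comes through a shunt (A1) or through the participant's own intraventricular catheter (E1). A child without one contributes no pair.
3. 2.a excludes other abnormalities affecting brain topology or function. Beside an inclusion criterion of craniosynostosis, *other* naturally means other than craniosynostosis.
4. Two groups of catheter-bearing children follow:
   - Catheter placed for a separate brain condition: excluded by 2.a, with no exemption.
   - Catheter placed for pressure attributed to the craniosynostosis itself: no *other* abnormality on this text, so not excluded by this criterion.
5. The documents do not give the sizes of these groups. On the second, A1 says that preoperative ICP monitoring is not routine, B2 says that ICP is rarely measured in craniosynostosis, and the one monitoring series described in B1 used an epidural sensor. This suggests a small group, but not an empty one.

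**Size under an assumed share**

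Let q be the assumed share of catheter-bearing children whose underlying condition falls under the exclusion. Then pairs left = N × (1 − q). N = 10 is A1's count. N = 12 is E1's ceiling and supposes that all twelve have a catheter, which E1 does not say.

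| Assumed q | N = 10 | N = 12 |
|---|---|---|
| 0 | 10 | 12 |
| 0.5 | 5 | 6 |
| 0.8 | 2 | 2.4 |
| 1 | 0 | 0 |

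The smallest absolute correlation that reaches significance is t / √(n − 2 + t²), where t is the 97.5% point on n − 2 degrees of freedom. A two-sided 5% level is assumed, since the plan states none.

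- n = 12: 2.228 / √(10 + 4.964) = 0.576
- n = 10: 2.306 / √(8 + 5.318) = 0.632
- n = 5: 3.182 / √(3 + 10.125) = 0.878
- n = 3: 0.997
- n = 2: no degrees of freedom remain, so no test is possible

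If half of ten children were excluded, the observed correlation needed for significance would rise from 0.632 to 0.878. At q = 0.8 the hypothesis could not be tested.

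**The case against.** The strongest objection is that the criterion excludes a history of other abnormalities, not the catheter. That every child with a catheter has such an abnormality is a clinical inference; hydrocephalus, for instance, appears in the documents only in a reference title. The protocol's own premise is that craniosynostosis may itself raise ICP, and E1 evidently expects some enrolled patients to have a catheter. This stands, and it limits what can be claimed.

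A reader might infer that no eligible child can have a direct ICP value. That is the q = 1 case. The documents do not support it, because a catheter placed for pressure attributed to the craniosynostosis does not trigger the exclusion, and *rarely measured* does not mean never.

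A reader might also infer that up to 10 of 12 cases would carry a second brain condition into the case-control contrast. That takes its numerator from A1 and its denominator from E1, which describe different populations. A1 does not say that its ten shunted children have craniosynostosis.

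The confounding argument is likewise conditional. It requires children to be enrolled against the exclusion, which no section suggests, and G3 and G4 describe exploratory comparisons with no specified test.

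Finally, the more certain defect is that A1, E1 and the inclusion list describe different populations, and 2.a never asks for a catheter. That is fair, and the two matters should be settled together. It does not remove this point, since correcting the inclusion list alone would leave the exclusion in force.

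**Conclusion.** The concern holds in a limited form. As written, the exclusion may remove many or most of the children in whom the reference measurement for A2 can be obtained. It conflicts with A1's shunted sample and E1's catheter-based reading. The wording of the criterion and the absence of an exemption are certain. The share of children affected is not: of A1's ten, anywhere from 10 pairs (q = 0) to none (q = 1) could remain, with 5 at q = 0.5 and 2 at q = 0.8. The documents give no basis for choosing q. The conclusion assumes that at least some catheters were placed for a condition other than the craniosynostosis, which is plausible but unstated. Because the sole primary hypothesis depends on these pairs, the point should be settled before screening begins.

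**What to change.** Reconcile A1, E1 and both lists in 2.a, so that one population is defined for each purpose.

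- **MRI-versus-direct-ICP correlation:** state that the eligible population includes children with a shunt or catheter, and that the condition for which it was placed is not an exclusion for this part. State also whether these children must have craniosynostosis.
- **G3 case-control contrast:** keep the exclusion as written. Leave out of this contrast, or show separately, any child with such a second condition.

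The exemption needs about two sentences in 2.a and one in G3, plus the edits that bring A1, E1 and the inclusion list into line. It adds no procedures. The exemption alone would not be enough: while inclusion stays limited to unrepaired single-suture craniosynostosis, A1's shunted children would not qualify unless they also had that diagnosis.

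The cost is fewer cases in the exploratory case-control contrast, possibly many fewer if most enrolled cases have a catheter placed for another condition. The protocol should say so and, if that contrast is still wanted, state how many cases without a second condition it needs.

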MR spectroscopy (MRS) will be used to obtain concentrations of N-acetyl aspartate (NAA) and lactate. NAA is a highly sensitive marker of brain injury and the presence of lactate can indicate compromised metabolism. We will measure whole-brain oxygen extraction (OEF) using a magnetic field mapping approach. Elevated OEF is a key indicator of compromised perfusion. Cerebral blood flow (CBF) will be measured using an arterial spin labeling (ASL) sequence, which will allow direct measurement of perfusion deficiencies. We will also obtain functional connectivity data using an rfcMRI sequence, which is sensitive to developmental delay. The analysis for OEF and ASL data will be performed by [name]. The MRI images will be read by [name], Chief of Radiology at Saint Louis Children's Hospital. Measures will include location and severity of metabolic effects, size of the optic nerve sheath, and cerebral perfusion.

G Statistical Plan

G1 Sample Size Determination and Power

As this is a pilot study there is no relevant data to determine the power of this study. The data collected here will be used as a guide for sample size determination of future studies.

G2 Interim Monitoring and Early Stopping

N/A

G3 Analysis Plan

The data obtained from the pilot study will be evaluated for patterns in the data between the subjects with craniosynostosis and the matched controls.

G4 Statistical Methods

Various graphical and image analysis approaches will be applied to tease out potential patterns between cases and controls and between the affected and unaffected sides of patients with unilateral craniosynostosis.

H Data Handling and Record Keeping

H1 Confidentiality and Security

Privacy during the recruitment and consent process will be protected by performing these procedures in private patient rooms in the hospital or clinic setting.

The MRI will be performed in the Center for Clinical Imaging Research (CCIR). No unnecessary PHI will be collected. Data will be a coded.

H2 Training

All members of the research team will be familiar with this protocol and the standard prosecution of clinical trials.

H3 Records Retention

Patient records will be stored behind a double lock system in the craniofacial laboratory in the division of Plastic Surgery.

I Study Administration

I1 Organization and Participating Centers

Division of Plastic Surgery in cooperation with the Department of Radiology

I2 Funding Source and Conflicts of Interest

None at this time.

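### Head trauma is an explicit exclusion for controls but not for cases, an unequal selection rule that could distort the exploratory case-control comparison in either direction

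*Combined protocol and SAP*

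**What the plan says.** E2 2.a lists three exclusions. Two are not limited to a group: implants that prevent MR scanning, and "History of other abnormalities known to affect brain topology or function". The third is for controls alone: "Control subjects must have no history of craniofacial abnormality or head trauma".

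The inclusion criteria are "Subjects presenting to the Plastic Surgery clinic with unrepaired single-suture craniosynostosis" and "Age-matched controls"; E1 adds gender to the matching. Neither mentions head trauma. Nothing in the document says that trauma history will be recorded, matched on or adjusted for in cases.

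E1 allows controls from the plastic surgery clinic, or that "deidentified data from normal subjects from another study will be used". It does not say what head-trauma rule that other study applied.

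On the measures, F4 says "NAA is a highly sensitive marker of brain injury", and D1 says "The MR sequences for this study have been used in studies of traumatic brain injury". G3 says the pilot data will be "evaluated for patterns in the data between the subjects with craniosynostosis and the matched controls", and G4 adds graphical and image analysis of the same contrast.

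**The concern.** Restricting the craniofacial exclusion to controls is unavoidable, because cases have such an abnormality by definition. Head trauma has no such reason. Controls must be free of any history of it, while cases need only be free of a known abnormality affecting the brain. Controls are thus cleared of one possible cause of altered readings that may remain among cases.

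At stake is how a case-control pattern is interpreted. If some cases carry the effect of an old injury, a difference in NAA, for example, could partly reflect that injury rather than craniosynostosis. The comparison is exploratory, but it is the whole of G3 and part of G4, and G1 intends the data to guide the sample size of later studies. Trauma history is not planned to be collected, so the question could not be settled afterwards from the study's own data.

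**Working it through.** The plan gives no trauma rate, no trauma effect, no SD and no power calculation, so there is no stated figure to reproduce. The check is mainly a reading of the criteria; the arithmetic is illustrative.

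**Step 1: apply the criteria to the same child in each role.**

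| History | As a case | As a recruited control |
|---|---|---|
| No head trauma | Eligible | Eligible |
| Head trauma, no known brain effect | Eligible | Excluded by the control-only rule |
| Head trauma, known brain effect | Excluded if the effect counts as an abnormality under the general exclusion | Excluded |

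The second row is the gap. The third is uncertain for cases only because the text does not say whether trauma counts as an abnormality.

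**Step 2: which measures are exposed.** F4 attaches the brain-injury label to NAA alone. It ties lactate to metabolism, OEF and CBF to perfusion, and functional connectivity to developmental delay. By their titles, references 6 and 7 concern oxygen metabolism and oxygen extraction in paediatric traumatic brain injury, which gives some support for adding OEF.

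**Step 3: direction.** F4 treats raised OEF as the sign of compromised perfusion. The title of reference 7 speaks of depressed OEF in paediatric trauma. If trauma lowers OEF, a case with past trauma would offset the rise being looked for. If trauma alters NAA, it could create a difference. No direction is given for trauma on lactate or CBF.

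**Step 4: size, on assumed inputs.** Let p be the proportion of cases with a trauma history, s the shift in a measure in SD units, and 0 the proportion in controls. Expected bias in the case-control difference = p × s. Chance of at least one such case among n = 1 − (1 − p)^n. E1 gives up to 12 cases; A1 gives ten children. The values of p and s are assumptions.

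| p | At least one of 12 | At least one of 10 | Bias, s = 0.5 | s = 1 | s = 2 |
|---|---|---|---|---|---|
| 2% | 21.5% | 18.3% | 0.01 SD | 0.02 SD | 0.04 SD |
| 5% | 46.0% | 40.1% | 0.025 SD | 0.05 SD | 0.10 SD |
| 10% | 71.8% | 65.1% | 0.05 SD | 0.10 SD | 0.20 SD |
| 20% | 93.1% | 89.3% | 0.10 SD | 0.20 SD | 0.40 SD |

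For example, 1 − 0.95^12 = 0.460, and 0.05 × 2 = 0.10 SD.

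In one realised sample of 12, k such children move the case mean by k × s/12. One child gives 0.5/12 = 0.04 SD to 2/12 = 0.17 SD; two give 0.08 to 0.33 SD.

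For scale, with 12 per group (control number assumed), a two-sided 5% test with 80% power detects about (1.960 + 0.842) × √(2/12) = 1.14 SD by the normal approximation. The plan specifies no such test.

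If the trauma proportion q in controls is not zero, the bias becomes (p − q) × s. Archived controls may have q above zero, because their source's rule is unknown.

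**Step 5: which analyses are exposed.** A2 correlates MRI and direct ICP within patients. The G4 side-to-side comparison is also within patients. Neither uses controls. Only the case-control contrast is exposed, and E1 makes that contrast optional.

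**The case against.** The strongest reply is that the general exclusion already does most of the work. It has no group limit, and read naturally it removes a case whose injury affected the brain, which is the trauma most likely to move these measures. This largely stands. It does not close the gap: the same bullet also applies to controls, so naming head trauma again for them would be redundant if it were already fully covered. Controls face the stricter test.

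A second reply is that the reach is limited. The contrast is optional in E1, exploratory, has no specified test, and is separate from the primary hypothesis. This stands, and it limits the importance of the point.

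A third is that excluding every child under eight with any bump to the head could cost cases in a sample of at most 12. This also stands, and it shapes the fix.

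A reader might go further and infer any of the following; the documents support none of them:

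- Cases with brain-affecting trauma enter freely. The general exclusion plausibly removes them.
- All outcome measures are brain-injury markers. F4 says so of NAA only.
- The bias always favours finding abnormality in cases. The OEF example in step 3 points the other way.
- A large shift such as 2 SD is to be expected. Nothing supports that for trauma with no known brain effect.

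**Conclusion.** The unequal rule is real and is stated in the text; it is not merely a missing detail. A child with past head trauma and no known brain effect can be a case but not a recruited control, and nothing planned would reveal how many such children there are. The G3/G4 comparison could be distorted in either direction.

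The size is unknown and probably small. With rates up to 10% and shifts up to 1 SD, the expected bias is at most 0.10 SD, against a detectable difference of about 1.14 SD. The extreme corner of the assumed grid (20%, 2 SD) gives 0.40 SD. These figures assume no trauma history among controls and a fixed shift in every affected child. In a graphical search for patterns in about 12 children, a single unusual child can still be conspicuous.

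A reader might infer that the primary result is compromised. It is not by this asymmetry, and neither is the side-to-side comparison. The point merits a change to the criteria but is no reason to hold up the study.

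**What to change.** 1. Apply one and the same head-trauma criterion to cases and controls, and keep craniofacial abnormality as a control-only exclusion. Say what counts as head trauma, with the threshold set by the clinical investigators, and whether the general exclusion is meant to cover it. Example wording: *No subject may have a history of head trauma as defined in this protocol; control subjects must also have no history of craniofacial abnormality.*
2. Record head-trauma history, including events below that threshold, for all recruited subjects, so that the case-control comparison can be repeated without affected children.
3. Use archived normal data only where the source study applied the same head-trauma criterion.

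If the criterion is ascertained equally in both groups, the expected bias from unequal selection is zero in every scenario above. The cost is an eligibility amendment, one screening question to the parent, an occasional case turned away, and possibly fewer usable archived scans.

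### The plan does not state that the MRI reader and analyst are masked to the direct ICP value, so a reader-dependent MRI measure could yield an inflated correlation with ICP

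*Combined protocol and SAP*

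**What the plan says.** A2 sets the result the study looks for: "Indirect (via MRI) and direct measures of ICP will have a significant positive correlation". The direct value is the reference and the MRI value is the index being tested against it.

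F4 describes how the MRI values arise. "The MRI images will be read by" one radiologist, and the section goes on: "Measures will include location and severity of metabolic effects, size of the optic nerve sheath, and cerebral perfusion". OEF and ASL analysis is assigned to another person. F4 gives no measurement procedure for the optic nerve sheath, no second reader, and no statement of what either person may know when producing the values.

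E1 places the direct measurement close to the scan: "Secondly, during the same visit, a transducer will be attached to the participant's intraventricular catheter if it is not already in place". The scan is listed first and the transducer second. When the images are read is not stated.

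G3 and G4 plan a search for "patterns in the data between the subjects with craniosynostosis and the matched controls", and also compare affected with unaffected sides. For controls, E1 allows that "deidentified data from normal subjects from another study will be used".

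The nearest thing to a safeguard is in H1: "Data will be a coded". It stands under confidentiality and does not address what the reader sees.

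**The concern.** When an index test is read by someone who knows the reference result, the two are no longer independent, and agreement can be inflated by expectation alone. The direct ICP value can exist before the images are read, because both belong to one visit and reading time is not fixed. Nothing in the plan keeps the value from the reader.

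This bears on A2. An inflated correlation would also carry forward: G1 says the data will guide the size of later studies, and a correlation that is too high would make the next study too small. Section J plans publication, and A1 links the work to possible changes in surgical indications.

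A related exposure exists for G3 and G4, where knowledge of group or affected side could colour an open-ended search for patterns. It is secondary here, because masking to group is only partly feasible.

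**Working it through.** **Text check.** The whole document was read for masking, blinding, independent reading and reading order. None is mentioned. The documents give no alpha, sidedness, power or effect size, so there is no planned figure to reproduce.

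**Illustration.** It applies only if the MRI measure correlated with ICP is reader-dependent.

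Inputs:
- n = 10 (A1); n = 12 is shown as well because E1 allows up to 12.
- True correlation 0 (assumed).
- Two-sided alpha 0.05 (assumed), so 2.5% in the positive direction.
- Reading = noise + b × direct ICP, with ICP and noise both of SD 1. Here b is the shift in the reading, in SDs, per SD of known ICP. Its range is assumed.

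Critical correlation: r_c = t / √(n − 2 + t²), with t the 97.5% point on n − 2 degrees of freedom.
- n = 10: t = 2.306, r_c = 2.306 / √(8 + 5.318) = 0.632.
- n = 12: t = 2.228, r_c = 2.228 / √(10 + 4.964) = 0.576.

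Induced correlation: r = b / √(1 + b²).
- b = 0.2: 0.2 / √1.04 = 0.196.
- b = 0.5: 0.5 / √1.25 = 0.447.

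Chance that the sample correlation exceeds r_c, by simulation (at least 200,000 replicates for the rows at b = 0, 0.25, 0.5, 0.75 and 1.0; the b = 0.2 row comes from separate runs of the same model):

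| b | Induced r | n = 10 | n = 12 |
|---|---|---|---|
| 0 (masked) | 0 | 2.5% | 2.5% |
| 0.2 | 0.196 | 7.6% | 8.7% |
| 0.25 | 0.243 | 9.6% | 11.3% |
| 0.5 | 0.447 | 26.1% | 32.0% |
| 0.75 | 0.600 | 48.5% | 58.2% |
| 1.0 | 0.707 | 69.4% | 79.1% |

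At b = 0.2 the false-positive chance roughly triples, yet about 92% of such studies (100 − 7.6) would still show no significant positive result. A large effect needs a moderate to large shift.

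**The case against.** Several stronger readings are tempting, and the documents do not support them.

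- *The read is unmasked.* A reader might infer this from the silence. The plan never says that the radiologist receives the ICP value; masking is unstated, not shown to be absent.
- *The measures are subjective.* F4 gives no method for sizing the optic nerve sheath, so manual measurement is an inference. Metabolic severity could be derived from the NAA, lactate, OEF and CBF values listed just before it. The sentence listing the measures is not expressly tied to the radiologist, and it includes perfusion, whose ASL analysis is assigned elsewhere.
- *The A2 correlation is therefore at risk.* No section says which MRI measure stands for ICP. If it is a computed value, this reader's expectation has little route in. G3 and G4 plan no correlation test.
- *Scanning first gives no protection.* It gives some, though not enough: the catheter or transducer may already be in use, and reading can follow the visit. A transducer in place does not show that the reader knows the value.
- *A small expectation effect would produce significance.* The table does not bear this out, and the size of b has no basis in the documents.
- *The case-control contrast is biased in the same way.* This is not quantified. Nothing says that this radiologist reads external control data, and skull shape or a catheter may reveal group whatever is done.

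These objections narrow the point without removing it. Independence of the index reading from the reference is not secured anywhere in the plan. Pilot status does not excuse that, since the estimate is meant to inform later studies.

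**Conclusion.** The concern holds in a conditional form. As written, the plan leaves the MRI reading open to knowledge of the ICP value with which A2 correlates it. To the extent that the MRI measure depends on judgement, that knowledge could inflate the correlation. Exposure is greatest for severity and sheath size if these are reader-scored, and smaller for computed values, although their analyst is not stated to be masked either.

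The rise from 2.5% to between about 8% and 26% at n = 10 is illustrative only. It rests on no true association, two-sided alpha 0.05 and an assumed shift of 0.2 to 0.5 SD per SD of ICP. The bias is possible, not demonstrated. The change should still be made, because it is a concrete step in conduct that costs almost nothing and cannot be restored after an unmasked read without re-reading the images.

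**What to change.** In F4, state that the same radiologist and the OEF/ASL analyst score coded images without access to the direct ICP value, and that MRI values are recorded and locked before they are merged with ICP. Where feasible, also withhold case or control status and affected side, and acknowledge that skull shape or a visible catheter may reveal group.

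The coding mentioned in H1 can be used for this. No extra reader, patient or scan is required. The small downside is a locked research read kept separate from any clinical report. The documents do not say whether the same radiologist also reports the clinical scan; if so, the research values need to be recorded before the ICP value is seen.
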